## **8.6 Exploratory Assessment of Correlative Immunologic Research**

Please refer to the Study Laboratory Manual for information on testing to be done and instructions on specimen handling and logistics.

---

CONFIDENTIAL

## 8.7 ECOG Performance Status

### Eastern Cooperative Oncology Group Performance Status

Grade	ECOG PS
0	Fully active, able to carry on all pre-disease performance without restriction
1	Restricted in physically strenuous activity but ambulatory and able to carry out work of a light or sedentary nature, e.g., light house work, office work
2	Ambulatory and capable of all self-care but unable to carry out any work activities. Up and about more than 50% of waking hours
3	Capable of only limited self-care, confined to bed or chair more than 50% of waking hours
4	Completely disabled. Cannot carry on any self-care. Totally confined to bed or chair
5	Dead

Reference: (39)

---

CONFIDENTIAL

## 8.8 List of Abbreviations

AE	adverse event
AESI	adverse event of special interest
ALK	Anaplastic lymphoma kinase
ALT	alanine aminotransferase
AST	aspartate aminotransferase
CD	Cluster of differentiation
CI	confidence intervals
CR	Complete response
CRF	Case report form
CTC	Circulating tumor cell
CTCAE	Common Terminology Criteria for Adverse Events
CTLA-4	Cytotoxic T lymphocyte-associated antigen 4
DC	Dendritic cell
DCR	Disease Control Rate
DLT	Dose limiting toxicity
DoR	Duration of response
ECG	electrocardiogram
ECOG	Eastern Cooperative Oncology Group
eCRF	Electronic Case Report Form
EGFR	epidermal growth factor receptor
FDA	Food and Drug Administration
FDG-PET	fluorodeoxyglucose (FDG)-positron emission tomography (PET)
FNA	Fine needle aspiration
FFPE	Formalin-fixed paraffin-embedded
GCP	Good Clinical Practice
GMP	Good manufacturing practice
HCC	hepatocellular carcinoma
IB	Investigator Brochure
ICF	Informed Consent Form
ICH	International Conference on Harmonization
IHC	Immunohistochemistry
ICS	intracellular cytokine staining
IL	interleukin
ILD	Interstitial lung disease
IND	Investigational new drug
IMP	Investigational medicinal product
IP	Investigational product
irAE	Immune-related adverse event
irRC	immune-related response criteria

---

CONFIDENTIAL

irRECIST	Immune-related Response Evaluation Criteria in Solid Tumors
IV	intravenous
IRB	Institutional Review Board
LICR	Ludwig Institute for Cancer Research
mAb	Monoclonal antibody
MDSC	myeloid derived suppressor cells
MedDRA	Medical Dictionary for Regulatory Activities
MTD	maximum tolerated dose
NCI CTCAE	National Cancer Institute Common Terminology Criteria for Adverse Events
NSCLC	Non-small cell lung cancer
NK	Natural killer
ORR	Objective Response Rate
OS	Overall survival
OVA	ovalbumin
PBMC	Peripheral blood mononuclear cell
PD	Progressive disease
PD-1	Programmed death-1
PD-L1	Programmed death ligand 1
PFS	Progression free survival
PK	Pharmacokinetics
PR	Partial response
Q4W	Every 4 weeks
QTc	corrected QT interval
RECIST	Response Evaluation Criteria in Solid Tumors
RCC	Renal cell carcinoma
RCD	Recommended combination dose
SAE	Serious Adverse Event
SCCHN	squamous cell carcinoma of the head and neck
SD	Stable disease
TAA	Tumor-associated antigens
TIL	tumor-infiltrating lymphocyte
TME	Tumor microenvironment
TMTB	Total Measured Tumor Burden
Tregs	regulatory T-cells
ULN	Upper limit of normal
WFI	Water for Injection

---

CONFIDENTIAL

## ACRONYMS

Below is the list of acronyms that will be used throughout this document.

Abbreviation	Definition
AE	adverse event
AESI	adverse event of special interest
CI	confidence intervals
CR	Complete response
CTCAE V.4.03	Common Terminology Criteria for Adverse Events v. 4.03
CTLA-4	Cytotoxic T lymphocyte-associated antigen 4
DNA	Deoxyribonucleic Acid
DCR	Disease Control Rate
DLT	Dose limiting toxicity
DoR	Duration of response
ECG	electrocardiogram
ECOG	Eastern Cooperative Oncology Group
FFPE	Formalin-fixed paraffin-embedded
GCP	Good Clinical Practice
ICH	International Conference on Harmonization
ILD	Interstitial lung disease
irRECIST	Immune-related Response Evaluation Criteria in Solid Tumors
MedDRA	Medical Dictionary for Regulatory Activities
NCI CTCAE	National Cancer Institute Common Terminology Criteria for
NSCLC	Non-small cell lung cancer
ORR	Objective Response Rate
OS	Overall survival
PBMC	Peripheral blood mononuclear cell
PD	Progressive disease
PD-L1	Programmed death ligand 1
PFS	Progression free survival
PR	Partial response
Q4W	Every 4 weeks
RECIST	Response Evaluation Criteria in Solid Tumors
RCD	Recommended combination dose
RNA	Ribonucleic Acid
SAE	Serious Adverse Event
SD	Stable disease
TEAE	Treatment Emergent Adverse Event
TIL	tumor-infiltrating lymphocyte
TME	Tumor microenvironment

## 1.0 PURPOSE

This SAP describes the methods to be used in the analysis of trial data from clinical protocol “A Phase 1/2 Study of Combination Immunotherapy and mRNA Vaccine in Subjects with Non-small Cell Lung Cancer (NSCLC)” in order to answer the trial objective(s), and is based on Amendment 9.1 of the trial protocol (LUD2014-012-VAC), dated 01 September 2020.

Populations for analysis, data handling rules, statistical methods, and formats for data presentation are described within this document. The statistical analyses and summary tabulations described in this SAP will provide the basis for the results sections of the CSR for this trial. The SAP outlines any differences in data analysis methods relative to those planned in the trial protocol. Any changes to the data analysis methods after the SAP is finalized will be described in the CSR.

## 2.0 OVERALL STUDY DESIGN AND OBJECTIVES

### 2.1 Trial Objectives

This study will evaluate the safety and efficacy of the addition of a vaccine therapy (BI 1361849, previously known as CV9202) to 1 or 2 checkpoint inhibitors (durvalumab and tremelimumab) for NSCLC. The study has two phases; the dose evaluation phase and the dose expansion phase. In the dose expansion phase, there are two cohorts as follows:

Arm A: mRNA Vaccine [BI 1361849 (formerly CV9202)] + anti-PD-L1 [durvalumab]

Arm B: mRNA Vaccine [BI 1361849] + anti-PD-L1 [durvalumab] + anti-CTLA-4 [tremelimumab].

The primary trial objectives are:

- Dose evaluation Phase: To evaluate safety and tolerability, including Dose Limiting Toxicities (DLTs) and Recommended Combination Dose (RCD) of a combination immunotherapy with durvalumab or durvalumab and tremelimumab together with an RNA vaccine BI 1361849.
- Expansion Phase: To evaluate safety and tolerability of a combination immunotherapy with durvalumab or durvalumab and tremelimumab together with an RNA vaccine BI 1361849.

The secondary trial objective is:

- To evaluate the clinical efficacy of the combination immunotherapy for all subjects in both the dose evaluation and the dose expansion phases.

The exploratory trial objective is:

- To evaluate Biologic Activity and the effects on tumor microenvironment, and immune response for all subjects in both the dose evaluation and the dose expansion phases.

## 2.2 Study Endpoints

### Primary Endpoints

The primary endpoint of the combination therapy of durvalumab and tremelimumab are:

- Dose- Limiting Toxicities (DLTs). DLTs are defined as any adverse events that are possibly, probably, or definitely related to the administration of durvalumab, tremelimumab, or BI 1361849 components. This applies to Dose Evaluation subjects during the DLT Evaluation period.
- Safety and tolerability evaluated using CTCAE 4.03.
- Recommended Combination Dose (RCD) determined in Dose Evaluation Phase.

The safety endpoints for this study include:

[figure not shown]
- Treatment-emergent adverse events (TEAEs) and serious AEs (SAEs)
- Clinical laboratory tests (hematology and chemistry)
- Vital signs and weight measurements
- ECG
- ECOG performance status evaluation
- Any other medically indicated assessments, including subject interviews
- All safety analyses will be reported separately for Arm A and Arm B

The Clinical efficacy endpoints will be assessed by irRECIST and RECIST 1.1 and will include:

- Objective Response rate (ORR) at 8 and 24 weeks. ORR is defined as the percentage of subjects meeting criteria of Complete Response (CR) or Partial Response (PR) over a period of at least 4 weeks.
- Duration of Response (DoR). DoR is defined as the interval between the date of earliest determination of CR or PR to the date of earliest determination of PD, or to the date of death, if PD does not occur.
- Disease Control rate (DCR). DCR is defined as the percentage of subjects meeting criteria of Stable Disease (SD), PR, or CR over a period of at least 4 weeks.
- Progressive Free Survival (PFS) at 8 and 24 weeks. PFS is defined as the interval between the date of first dose to the date of earliest determination of Progressive Disease

(PD), or to the date of death, if PD does not occur. Week 8 corresponds to Cycle 3 Day 1 and Week 24 corresponds to Cycle 7 Day 1.

- Overall Survival (OS). OS is defined as the interval between the date of first dose until the date of death or the date of last follow-up.
- All efficacy analyses will be reported separately for Arm A and Arm B.

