**Figure 2. Dose Escalation and De-Escalation Schema**

Per Figure 2, the RCD for Arm A and Arm B is defined as the highest dose level at which no more than 1 of 6 subjects (i.e., < 33%) experience DLTs. The RCD cannot be determined if none of the predefined dose level cohorts fulfill that criterion. In such case, the arm will be discontinued without an expansion phase.

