### 3.1.9 DLT and MTD/RCD for the Combination Therapy

MTDs will not be determined in this study. Instead, RCDs will be determined in the context of the predefined dose levels used during the dose evaluation phase as per Section 3.1.7.1.

DLTs will be observed over a period of the first 2 cycles of the combination therapy, including the pre-dose assessment for Cycle 3, defined as the **DLT Evaluation Period**. The decisions for dose evaluations, de-escalations and RCD, as described in Section 3.1.7.1 will primarily be based on the number of subjects with DLTs occurring during the DLT Evaluation Period. DLTs occurring outside the DLT Evaluation Period will also be evaluated and may impact such decisions.

DLTs are defined as any adverse events that are possibly, probably, or definitely related to the administration of durvalumab, tremelimumab, or BI 1361849 components, and fulfill any of the following criteria:

1. Any Grade  $\geq 3$  colitis, pneumonitis, neurological event or uveitis.
2. Any Grade 2 pneumonitis, neurological event or uveitis, with the following exception:
  - Grade 2 pneumonitis, neurological event or uveitis that downgrade to Grade  $\leq 1$  within 3 days after onset, whereby maximal supportive care, including systemic corticosteroids, is permitted.
3. Any *other* Grade  $\geq 3$  toxicity, with the following exceptions:
  - Grade 3 irAEs that downgrade to Grade  $\leq 2$  within 3 days, or to Grade  $\leq 1$  or baseline within 14 days after onset, whereby maximal supportive care, including systemic corticosteroids, is permitted.
  - Grade 3 endocrinopathy that becomes asymptomatic when managed with or without systemic corticosteroid therapy and/or hormone replacement therapy.
  - Grade 3 inflammatory reaction attributed to a local antitumor response (e.g., inflammatory reaction at sites of metastatic disease, lymph nodes, etc.).
  - Grade 3 fatigue for  $\leq 7$  days.
  - Grade 3 infusion-related reaction (first occurrence and in the absence of steroid prophylaxis) that resolves within 6 hours with appropriate clinical management.
  - Liver transaminase elevation  $\leq 8$  times ULN that downgrades to Grade  $\leq 2$  ( $\leq 5$  times ULN) within 7 days after onset, whereby maximal supportive care, including systemic corticosteroids, is permitted.

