  - Total bilirubin  $\leq 5$  times ULN that downgrades to Grade  $\leq 2$  ( $\leq 3$  times ULN) within 7 days after onset, whereby maximal supportive care, including systemic corticosteroids, is permitted.
  - Grade  $\geq 3$  neutropenia that (1) is not associated with fever or systemic infection, (2) does not require medical intervention, and (3) improves to Grade 2 within 7 days.
  - Grade 3 and 4 lymphopenia.
  - Grade 3 thrombocytopenia that (1) is not associated with clinically significant bleeding, (2) does not require medical intervention, and (3) improves to Grade 2 within 7 days.
  - Isolated Grade 3 electrolyte abnormalities that are not associated with clinical signs or symptoms and are reversed with appropriate maximal medical intervention within 3 days.
  - Any pre-existing laboratory abnormality that deteriorates to Grade 3/4, but where the increment of deterioration is considered not clinically significant by both investigator and sponsor.
  - Grade 3 or 4 asymptomatic increases in amylase or lipase levels for which appropriate evaluation shows no clinical evidence of pancreatitis.

Immune-related AEs (irAEs) are defined as AEs of immune nature (i.e., inflammatory) in the absence of a clear alternative etiology. In the absence of clinical abnormality, repeat laboratory testing will be conducted to confirm significant laboratory findings prior to designation as a DLT.

While rules for adjudicating DLTs are specified above, an AE that is Grade < 3 or listed as exempt above may also be defined as DLT after consultation with the sponsor and Investigators, based on the emerging safety profiles of durvalumab, tremelimumab, and BI 1361849. Likewise, subjects who become not evaluable for DLT, because they discontinued or interrupted treatment due to toxicities other than DLTs, may be counted as DLT subjects, if the toxicities cannot be managed in accordance with the dosing modifications described in Section 3.1.8.

Subjects who experience a DLT will be discontinued from study treatment and will enter the On Study and Post Study Follow-up (see Section 3.1.16). However, if it is in the best interest of the subject, the Investigator, subject and Sponsor may agree to continue treatment with BI 1361849.

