### 4.3 Per-Protocol Population (DLT Assessments)

The Per-Protocol (PP) Population (DLT Assessments) is defined as follows:

- All subjects in the dose escalation who experience a DLT at any time during the DLT Evaluation Period (as defined in Section 3.1.9 of the protocol).
- All subjects with no DLT who receive at least 75% of the scheduled doses of durvalumab and tremelimumab and at least 4 of the 5 BI 1361849 vaccinations over the first 2 cycles as well as respective safety assessments without major protocol violations during the DLT Evaluation Period .

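### SAP 2.2 defines a DLT, a primary endpoint, as any treatment-related AE in the DLT period, leaving out the criteria and exceptions of protocol 3.1.9 that nothing else in the SAP restores

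*SAP*

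**What the plan says.** SAP 2.2, under Primary Endpoints, gives this definition: "DLTs are defined as any adverse events that are possibly, probably, or definitely related to the administration of durvalumab, tremelimumab, or BI 1361849 components". The next sentence sets only its scope: "This applies to Dose Evaluation subjects during the DLT Evaluation period".

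Protocol 3.1.9 opens with the same relatedness clause, but its sentence continues: "and fulfill any of the following criteria". Three criteria follow:

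- Grade 3 or higher colitis, pneumonitis, neurological event or uveitis.
- Grade 2 pneumonitis, neurological event or uveitis, with one exception for rapid improvement.
- Any other Grade 3 or higher toxicity, with 13 listed exceptions.

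Protocol 3.1.9 then lets the sponsor and investigators designate further events as DLTs after consultation. It also says that subjects who become non-evaluable because of "toxicities other than DLTs, may be counted as DLT subjects" under a stated condition. On timing it says: "DLTs occurring outside the DLT Evaluation Period will also be evaluated and may impact such decisions".

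The DLT count feeds the RCD rule in protocol 3.1.7.1 (text under Figure 2), where the RCD is the "highest dose level at which no more than 1 of 6 subjects" with a DLT. SAP 1.0 says: "The SAP outlines any differences in data analysis methods relative to those planned in the trial protocol".

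**The concern.** DLTs are a primary endpoint of the dose evaluation phase, and SAP 1.0 makes the SAP the basis for the results sections of the clinical study report. A programmer who follows SAP 2.2 as written would flag every related AE in the first two cycles as a DLT, whatever its grade.

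Two outputs would change. The DLT table and listing ordered in SAP 9.1.1 would be inflated by mild events, so the report could show more DLTs than the RCD rule permits at the dose level that was declared the RCD. The per-protocol population for DLT would also widen. Its first limb in SAP 4.3 admits "All subjects in the dose escalation who experience a DLT at any time during the DLT Evaluation Period", so a subject who missed the dosing requirement of the second limb but had one mild related AE would now qualify.

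**Working it through.** **Is the definition completed elsewhere in the SAP?** These are the other places where the SAP uses the term:

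| SAP section | Use of DLT | Gives or cites the criteria? |
|---|---|---|
| 2.1 | Named in the primary objective | No |
| 4.3 | First limb of the PP population; cites protocol 3.1.9 | No, the citation is for the evaluation period |
| 5.0 | Reason for ending treatment | No |
| 9.1.1 | Table and listing ordered | No |
| 11.1 | Replacement of non-evaluable subjects | No |
| 11.7 | Interim safety reviews | No |

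The citation in SAP 4.3 is the nearest candidate. It stands in a parenthesis directly after the evaluation period. Protocol 4.1.2 attaches the same parenthesis to the period in its bullet for subjects without a DLT, where it can only define the period.

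**Is it a version difference?** The SAP is based on Amendment 9.1. The last change to 3.1.9 recorded in the protocol's version history is in Amendment 3 (October 2017), which added one exception. Different amendments therefore do not explain the gap.

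**What does the literal definition amount to?** SAP 9.1 counts a TEAE as related if it is rated definitely, probably or possibly related. SAP 2.2 applies the same test to a DLT. Read literally, a DLT is a treatment-related AE of any grade in the first two cycles.

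**How large could the effect be?** The documents give no rate for related AEs in this window, so what follows is an illustration. Let p be the proportion of subjects counted as having a DLT, and treat 6 subjects as independent:

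- Expected number of 6 = 6p
- P(at most 1 of 6) = (1 − p)^6 + 6p(1 − p)^5

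Two reference values come from the summary of Trial CV-9202-006 in protocol 1.2.3. There, 25 of 26 subjects (96.2%) had a vaccine-related AE. Three related Grade 3 AEs were reported, so at most 3 of 26 subjects (11.5%) had one.

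| p | Source | Expected of 6 | P(at most 1 of 6) |
|---|---|---|---|
| 0.50 | assumed | 3.0 | 0.109 |
| 0.60 | assumed | 3.6 | 0.041 |
| 0.80 | assumed | 4.8 | 0.0016 |
| 0.90 | assumed | 5.4 | 0.000055 |
| 25/26 | any related AE, earlier trial | 5.8 | 0.00000049 |
| 3/26 | related Grade 3, earlier trial | 0.7 | 0.854 |

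For example, at p = 0.5 the chance is (1 + 6)/64 = 0.109. At p = 25/26 it is (1 + 150)/26^6 = 151/308,915,776 = 4.9 × 10⁻⁷.

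Over the exact 95% interval for 25/26 (0.804 to 0.999), the chance runs from 0.0015 to 5 × 10⁻¹⁵. Over that for 3/26 (0.024 to 0.302), it runs from 0.99 to 0.42.

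**The case against.** The strongest reply is that this is a shortened sentence and not a redefinition. SAP 9.1.1 orders treatment-related AEs, related AEs of Grade 3 or higher, and DLTs as separate outputs; under the literal reading the DLT table would only repeat related AEs for a subset of subjects and time. SAP 5.0 lists a DLT at any time as a reason for ending treatment, which cannot be meant for every Grade 1 related event. The SAP declares no departure from the protocol, so the protocol definition can be presumed to stand. DLT status is settled by consultation and safety review, so harm arises only if someone ignores the adjudicated DLTs and derives new ones from the relatedness field.

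This shows that the truncation is probably unintended. It does not make the written rule correct. SAP 2.2 is phrased as a complete definition of a primary endpoint, and a reader should not have to infer from the table list that it cannot mean what it says.

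The caution about the figures also stands. Trial CV-9202-006 ran for up to 806 days with about 8.6 vaccinations per subject at 1920 µg, against 5 vaccinations at 960 µg in this window, and without checkpoint inhibitors. Nor is 3/26 a DLT rate: short Grade 3 fatigue is exempt under 3.1.9, and some Grade 2 events count.

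Finally, a bare cross-reference would repair the definition. Listing late DLTs separately goes a little further, but protocol 3.1.9 says these events will also be evaluated.

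**Conclusion.** The concern holds. SAP 2.2 states a rule for a primary endpoint that differs from protocol 3.1.9, the difference is not declared, and no other SAP section corrects it. This conclusion rests on comparing the texts and needs no assumption about event rates.

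The consequence is limited to what would be reported: the DLT endpoint, its table and listing, and membership of the per-protocol population for DLT. Dose and RCD decisions run under protocol 3.1.7.1 and 3.1.9 and are untouched.

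The size of the distortion depends on the unknown rate of any related AE in the first two cycles. At an assumed 50% to 96%, half to nearly all of 6 subjects would carry a DLT label. The two rates from the earlier trial show how much of that the missing grade criteria account for, but they are not estimates for this trial.

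**What to change.** In SAP 2.2, replace the definition with a direct reference to protocol 3.1.9. The reference should take in its criteria, its exceptions, the sponsor and investigator adjudication, and the rule under which subjects made non-evaluable by other toxicities may be counted as DLT subjects.

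State that the primary DLT endpoint, the DLT table in SAP 9.1.1 and the population in SAP 4.3 all use DLTs so defined within the DLT Evaluation Period. Flag DLTs that occur outside the period and list them separately.

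The cost is one cross-reference and one flag in the dataset. No new data are needed, and the protocol's own definition is left as it is.

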### 2.3 Trial Design and Trial Procedures

This is an open-label multicenter 2-arm study to evaluate the safety and preliminary efficacy of the addition of a vaccine therapy to 1 or 2 checkpoint inhibitors for NSCLC:

- Arm A: mRNA Vaccine [BI 1361849 (formerly CV9202)] + anti-PD-L1 [durvalumab].
- Arm B: mRNA Vaccine [BI 1361849] + anti-PD-L1 [durvalumab] + anti-CTLA-4 [tremelimumab].

For each arm of the study, there is a *dose evaluation phase* in which the Recommended Combination Dose (RCD) is determined according to a standard 3 + 3 design. For Arm A, the RCD of BI 1361849 + durvalumab is determined. The starting dose of durvalumab is 1500 mg with possible de-escalation to 750 mg; the dose for BI 1361849 remains constant at 12 x 80 ug. The 1500 mg Q4W dosing of durvalumab is recommended only for subjects with > 30kg body weight. Subjects with a body weight  $\leq$  30 kg are not eligible for enrollment in the current study. If a subject's body weight drops to  $\leq$  30 kg while on the study, the subject will receive weight-based dosing equivalent to 20 mg/kg of durvalumab as long as the body weight remains  $\leq$  30 kg. When the weight improves to >30 kg, the subject may return to fixed dosing of durvalumab 1500 mg.

[figure not shown]
For Arm B, the RCD of BI 1361849 + durvalumab from Arm A with the addition of tremelimumab 75 mg is evaluated. There is no dose escalation/de-escalation for Arm B; if there is unacceptable toxicity in Arm B, the arm will be discontinued as presented in Figure 1.

The *dose evaluation phase* is followed by an *expansion phase*, in which the cohort at the RCD for each arm is expanded to 20 subjects (inclusive of the subjects from the dose evaluation cohort i.e., 14 subjects will be added to the 6 treated at the RCD in the dose evaluation phase for each arm (A and B).

